### 3.1.2 ENGAGEMENT AND PROGRAM COMPLETION

Secondary objectives of the trial will be a) to compare engagement with digital vs. human coach-based DPPs and evaluate whether between-group differences in clinical outcomes are mediated by engagement and b) to compare acceptability of digital vs. human coach-based DPPs. We will define an engagement score (out of 100%) for the hDPP based on the percentage of total number of sessions attended, using the most current CDC engagement definitions at the time of completion of the study. Percentage engagement will be defined out of a total of 8 sessions in month 1-6 and 3 sessions in month 7-12, for a total of 11 sessions across months 1-12. We will define an engagement score (out of 100%) for the dDPPs based on percentage of full weeks during which the app is installed and a) both push notifications and motion sensors are enabled or b) the participant accesses any component within the app for months 1-6 and months 7-12. We hypothesize that participant's level of engagement, regardless of treatment assignment, will be associated with the primary endpoint (attainment of CDC benchmark for diabetes risk reduction). We hypothesize that dDPPs will be considered more acceptable by participants owing to greater convenience, more timely support, and the provision of more effective tools for weight, diet, and activity monitoring.

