## 9.2 SAMPLE SIZE DETERMINATION

Under a 1:1 randomization design, with a significance level (alpha) of 5% and 80% power, and assuming 50% of the participants achieve the primary outcome in both arms, 138 participants are required to enroll in each of the two arms, for a total study sample size of  $n = 276$ . Assuming a conservative attrition rate of 25% at 12 months, the adjusted sample size is set to 184 per group (368 total) to ensure the minimal necessary analyzable sample of 276 is retained. If there is truly no difference between the hDPP and dDPP, then 276 participants are required to be 80% sure that the upper limit of a one-sided 95% confidence interval will exclude a difference in favor of the hDPP of more than 15%. While it was previously noted that  $\pi_s$  will be closer to the 30-40% range, we used 50% in the non-inferiority sample size calculations as this choice yields the largest necessary sample size among all choices for  $\pi_s$ , and thus makes the study robust, in terms of statistical power, to other values for  $\pi_s$ .

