#### 9.4.8 ANALYSIS OF THE SECONDARY ENDPOINT(S)

Secondary endpoints will also be analyzed according to the ITT principle. Each of the individual outcomes in the CDC's benchmark for type 2 diabetes risk reduction (a composite endpoint) will be analyzed as a secondary endpoint at both the 6- and 12-month time points. As with the primary effectiveness endpoint, each outcome will be analyzed using logistic regression models. In addition, we will analyze change in A1C, absolute weight change and percentage weight change as continuous measures using linear regression models. Various physical activity measures will be analyzed as continuous measures, including average minutes/week of PA (light, moderate, intense), MET-hours per week of PA, and average number of steps per day. For responses from acceptability questionnaire (Likert-scale questions), non-parametric tests such as Spearman's correlation or chi-square test for independence will be used. For overall Likert scale scores, parametric tests such as Pearson's correlation or t-test will be used.

We anticipate that there will be a very low amount of missing data for the outcomes of A1C and weight for study completers, since both measures are collected by the research coordinator at the study visits. However, since the outcome of PA measurement relies on participants to wear the ActiGraph devices at 1-month intervals, there may be more missing data for this outcome variable. If more than 5% of data for this outcome variable is missing, the primary analysis will be based on multiple imputation. A sensitivity analysis will also be done using a complete case analysis (i.e. participants with 100% of valid PA data) and if results differ significantly, the primary analysis will be interpreted in light of results from the sensitivity analysis.

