## 11.10 ACCEPTABILITY QUESTIONNAIRE

## Acceptability Questionnaire (32-item)

[figure not shown]
Please rate your diabetes prevention program from strongly disagree to strongly agree to strongly agree:	Strongly disagree	Disagree	Neutral	Agree	Strongly agree
1. The [Sweetch DPP/ In-person DPP] gave me information and advice in an interesting way.	 1	 2	 3	 4	 5
2. I had fun using the [Sweetch DPP/ In-person DPP]	 1	 2	 3	 4	 5
3. The [Sweetch DPP / In-person DPP] motivated me to make lifestyle changes to prevent diabetes.	 1	 2	 3	 4	 5
4. The [Sweetch DPP/ In-person DPP] is appropriate for patients like me with pre-diabetes.	 1	 2	 3	 4	 5
5. I felt capable of meeting the expectations of the [Sweetch DPP/ In-person DPP]	 1	 2	 3	 4	 5
6. The [Sweetch DPP/ In-person DPP] helped me to become or stay active.	 1	 2	 3	 4	 5
7. The [Sweetch DPP/ In-person DPP] helped me to adhere to a healthy diet.	 1	 2	 3	 4	 5
8. The [Sweetch DPP/ In-person DPP] helped me to achieve or maintain a healthy body weight.	 1	 2	 3	 4	 5
9. The information collected by the [Sweetch DPP/ In-person DPP] would be useful for my doctor to see.	 1	 2	 3	 4	 5

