31A. For dDPP arm only: I think I would have preferred an in-person diabetes prevention program over the digital version.	 5	 4	 3	 2	 1
31B. For hDPP arm only: I think I would have preferred a digital diabetes prevention program over the in-person version.	 5	 4	 3	 2	 1
32. Please provide any comments regarding your overall experiences with the [dDPP or in-person DPP]					

Scoring: Sum up all responses to questions 1-31, divide by 155 and multiply by 100 to calculate percentage score out of 100%. Range of possible scores is 20% (lowest acceptability) to 100% (highest possible acceptability).

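### For the ordered acceptability items the plan offers a chi-square test that ignores ordering and, under assumed moderate shifts, costs about 18 to 23 points of power; a rank or proportional-odds analysis with an effect estimate should be named

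*Combined protocol and SAP*

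**What the plan says.** Acceptability is a listed secondary endpoint. Section 3.1.2 makes it a between-arm question, "to compare acceptability of digital vs. human coach-based DPPs", and gives a direction: "We hypothesize that dDPPs will be considered more acceptable by participants owing to greater convenience". Section 3.1.3 adds that the arms will be compared on several aspects, such as usefulness, ease of use and satisfaction.

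The questionnaire in section 11.10 uses five ordered responses scored 1 to 5 and is given at 6 and 12 months. It defines one overall score: "Sum up all responses to questions 1-31, divide by 155 and multiply by 100". Item 31 has two forms. 31A asks the digital arm whether an in-person programme would have been preferred, and 31B asks the coach-based arm the reverse.

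Section 9.4.8 treats items and total separately. For items, the examples of non-parametric tests are Spearman's "correlation or chi-square test for independence will be used". For the total, "For overall Likert scale scores, parametric tests such as" Pearson's correlation or a t-test are listed. The section does not say which item test compares the arms, what the correlation is taken against, what item-level effect is reported, or which visit carries the main comparison. No power is stated for acceptability.

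**The concern.** A test of independence on a 2x5 table gives the same result if the five columns are shuffled. It therefore ignores the fact that agreeing strongly is more favourable than agreeing. The hypothesis is that one programme is more acceptable, which is most simply a shift towards the favourable end. A test that uses the order concentrates on that shift with one degree of freedom, while chi-square spreads its sensitivity over four. Chi-square also yields no measure of how far the arms differ or in which direction.

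At stake is whether a real, moderate difference in acceptability is missed item by item. In addition, tests of quite different power stay open for choice in an open-label trial whose biostatistician is unmasked (section 6.4).

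**Working it through.** **The plan's own sample size.** Section 9.2 has success 50% in both arms, margin 15 points, one-sided 5% and 80% power: n = (1.645 + 0.842)² × 2 × 0.5 × 0.5 / 0.15² = 137.4, so 138 per arm. Allowing for 25% attrition, 138 / 0.75 = 184. Both figures reproduce. I use 138 as the analysable number per arm.

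**Assumptions, because the documents give none.** Item distributions, odds ratios and the proportional-odds form are mine. Tests are two-sided at 5%, following section 9.3.

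**Chi-square power, worked for one case.** Take 5/10/20/40/25% from least to most favourable in one arm. A common odds ratio of 1.5 gives 3.4/7.1/15.9/40.3/33.3% in the other. The noncentrality is n × Σ(p − q)²/(p + q) = 138 × 0.0245 = 3.38. The 5% critical value on 4 df is 9.49, and the power is 27%. The simulated value agrees (27.1%).

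**Comparison with the tie-corrected Wilcoxon rank-sum test** (same distribution, 138 per arm, 20,000 simulations per row):

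| Odds ratio | Chi-square, % | Rank-sum, % | Gap, points |
|---|---|---|---|
| 1.0 | 5.1 | 5.3 | – |
| 1.3 | 13.0 | 21.9 | 8.9 |
| 1.5 | 27.1 | 45.3 | 18.2 |
| 1.7 | 44.7 | 67.6 | 22.9 |
| 1.9 | 62.2 | 82.7 | 20.5 |
| 2.5 | 92.6 | 98.4 | 5.8 |
| 3.0 | 98.5 | 99.9 | 1.4 |

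Other item shapes give nearly the same gaps, with about 5 to 8 points at 2.5. With all 184 per arm analysed, the gap is about 21 to 22 points at 1.5, 10 to 13 at 2.0 and 1 to 3 at 2.5.

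**Why the size is generic.** 80% power on 1 df needs noncentrality (1.960 + 0.842)² = 7.85. The same noncentrality on 4 df gives 60%.

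**Spearman's correlation of item with arm.** With tied ranks, the squared rank-sum statistic equals (N − 1) × r². In one simulated data set with N = 276, r = 0.1505, so 275 × 0.1505² = 6.23, z = 2.50 and p = 0.0126. The usual Spearman p-value is 0.0123. Across all settings its power was within 0.1 point of the rank-sum test.

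**A pattern that is not a shift.** Take 10/20/40/20/10% against 20/15/30/15/20%. Both have mean score 3.0. The noncentrality is 138 × 0.0952 = 13.1. Chi-square has about 85% power and the rank-sum test 5%.

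**The case against.** The strongest reply is that the plan already contains most of what is wanted. Three parts of that reply stand.

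- The tests are given as examples, so a rank-sum test is not excluded.
- Spearman's correlation respects the ordering and, if taken against arm, is in effect the rank-sum test.
- The overall score has a t-test option, and section 9.4.1 plans linear regression for continuous secondary measures, so a between-arm difference in acceptability is available.

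A reader might therefore go too far in any of three directions. One is to say that every named item test loses about 20 points. That is true only of chi-square, and only for moderate shifts. Another is to say that acceptability has no between-arm effect estimate. The t-test on the total supplies one; what is missing is an item-level estimate. The third is to count 31 items at two visits as 62 planned tests, with 62 × 0.05 = 3.1 expected false positives if nothing differs. The plan does not commit to testing every item at every visit. Item 31 is also a different question in each arm, which leaves at most 30 × 2 = 60 tests on common wording. The count is an upper bound, not a feature of the plan.

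It is also fair that section 3.1.2 states a direction and not a proportional shift, and that chi-square would do better if one programme divided opinion. What remains is that one of only two named item tests is poorly matched to the stated hypothesis, and that the other is not tied to arm.

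**Conclusion.** The point holds in a limited form. If chi-square is the test used, power for an item falls by about 18 to 23 points at odds ratios of 1.5 to 1.9 with 138 per arm, by about 9 to 10 at 1.3, and by about 5 to 8 at 2.5. The loss reverses under polarisation. These figures rest on assumed item distributions and a proportional shift; the documents provide neither. If Spearman's correlation with arm is used there is no loss, but the plan does not say so and names no item-level effect estimate. Severity is low: acceptability is an unpowered secondary endpoint, and nothing here affects the non-inferiority conclusion.

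**What to change.** In section 9.4.8:

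- For between-arm comparisons of items, replace chi-square and the unspecified correlation with the Wilcoxon rank-sum test or a proportional-odds model, and report a common odds ratio with its confidence interval.
- Name the section 11.10 percentage score at 12 months as the main acceptability comparison, using the t-test already listed and reporting the mean difference with its confidence interval.
- Label item-level and month-6 results as descriptive.
- Do not compare item 31 between arms as if it were one question.
- If a correlation is wanted for another purpose, state both variables.

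The cost is a wording change, with no new data. The downside is less sensitivity to polarised differences, which a table of response percentages by arm would still show, and item results that no longer carry formal conclusions.

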## 3.2 PRIMARY ENDPOINT

The trial is designed as a non-inferiority trial to evaluate whether the Sweetch dDPP is at least as effective as hDPPs on participant attainment of the CDC's benchmark for type 2 diabetes risk reduction, defined as one or more of the following:

- At least 5% weight loss by 12 months
- At least 4% weight loss at 12 months and at least 150 minutes/week of physical activity measured using monthly serial Actigraphy and averaged over months 1-11)
- At least a 0.2% reduction in hemoglobin A1C by 12 months (for participants whose A1C result obtained at baseline study visit is between 5.7% and 6.4%).

Thus, the prospectively defined primary endpoint will be a binary endpoint at 12 months, defined as 1 if at least one of the CDC "success" outcome measures is achieved and 0 if none are achieved. The primary endpoint was selected to align with the current CDC standards for full recognition of DPP programs (effective May, 2021). According to the CDC, participants may demonstrate type 2 diabetes risk reduction by fulfilling one or more of the above outcomes, and, given the broad range of eligibility criteria for the DPP (see Section 5.1), not all DPP participants are eligible to demonstrate success using each of three outcomes in our composite endpoint. Specifically, the A1C change measure can only be used for participants whose baseline measure is in the prediabetic range of 5.7% to 6.4%. These standards require that at least 60% of participants in a given DPP meet the endpoint for attainment of full recognition in order to become a Medicare DPP supplier. The CDC's Standards and Operating Procedures are subject to change during the course of the study. Should the benchmarks for type 2 diabetes risk reduction change prior to completion of the trial, to the extent possible (i.e. assuming we have collected required data during the trial), we will also analyze our outcomes to align with the updated benchmark.

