## 9.3 POPULATIONS FOR ANALYSES

Consistent with the **intention-to-treat (ITT)** principle, results of all study participants will be evaluated according to initial randomization regardless of whether they adhered to their assigned treatment and regardless of protocol violations or deviations. Analyses of effectiveness endpoints, however, will exclude participants who withdraw from the study or withdraw consent. Effectiveness analyses will be performed for the ITT population. All primary statistical analyses of effectiveness measures will be unadjusted and two-sided tests of significance will be used. A per-protocol analysis will also be conducted using the population of program completers in each group, as defined in Section 3.3, to benchmark outcomes against CDC standards.

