#### 9.4.2 MISSING OUTCOMES DATA

We anticipate that there will be a very low amount of missing data for the outcomes of A1C and weight for study completers, since both measures are collected by the technician at the study visits. However, since the outcome of PA measurement relies on participants to wear the ActiGraph devices at 1-month intervals, there may be more missing data for this outcome variable. If more than 5% of data for this outcome variable is missing, the primary analysis will be based on multiple imputation. A sensitivity analysis will also be done using a complete case analysis (i.e. participants with 100% of PA data) and if results differ significantly, the primary analysis will be interpreted in light of results from the sensitivity analysis.

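### The complete-case set and the imputation trigger are defined on physical activity data, not on whether the primary composite is known

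*Combined protocol and SAP*

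**What the plan says.** Section 3.2 makes the primary endpoint binary: success if any of three routes is met, failure if none is. The routes are at least 5% weight loss; "At least 4% weight loss at 12 months and at least 150 minutes/week of physical activity", with activity averaged from monthly Actigraphy over months 1 to 11; and an A1C reduction of at least 0.2 points, open only to participants whose baseline A1C lies between 5.7% and 6.4%.

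Section 9.4.2 expects little missing weight or A1C among study completers and more missing PA. On the PA variable it says: "If more than 5% of data for this outcome variable is missing, the primary analysis will be based on multiple imputation". Section 9.4.8 repeats the rule almost unchanged and describes the sensitivity analysis as a "complete case analysis (i.e. participants with 100% of valid PA data"; the word valid appears only there. Both sections add that, if the two analyses differ significantly, the primary analysis is to be read against the sensitivity result.

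Four things are not stated: whether the 5% counts participants or wear periods, how many valid periods the months 1 to 11 average needs, what counts as a significant difference between the analyses, and how missing 12-month weight or A1C is handled.

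**The concern.** A complete-case analysis of the primary endpoint should keep everyone whose primary endpoint is observed. Here membership depends on a variable that most participants' status does not need. Someone with 8% weight loss and one missed wear week is a known success, yet is dropped.

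Those who remain are chosen by something that happens after randomisation. Section 3.1.2 hypothesises that engagement is associated with the primary endpoint. It is a reasonable inference, though not a stated fact, that full Actigraphy wear goes with engagement. The comparison in that subset is then no longer protected by randomisation, and in an open-label trial of two very different programmes the selection could differ by arm. The subset is also less precise, so it could look discordant with the primary analysis through loss of power alone.

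The trigger has the opposite fault. It reacts to PA gaps that leave the endpoint unchanged, and is silent on missing weight or A1C, which can leave the endpoint unknown.

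**Working it through.** **1. The plan's own figure.** Section 9.2 works "with a significance level (alpha) of 5% and 80% power". Its success rates come from "assuming 50% of the participants achieve the primary outcome in both arms". The aim is to be "80% sure that the upper limit of a one-sided 95% confidence interval" stays below the 15-point margin. Per arm, n = (1.645 + 0.842)² × (0.25 + 0.25) / 0.15² = 137.4, so 138. Then 138 / 0.75 = 184. Both stated figures (276 analyzable, 368 randomized) reproduce. Section 9.3 says "two-sided tests of significance will be used"; I keep the one-sided 5% level because it reproduces 138, and leave that inconsistency as a separate matter.

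**2. When PA matters (Section 3.2; no assumptions needed).** With 12-month weight and A1C observed:

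| Weight loss | A1C success | Status |
|---|---|---|
| 5% or more | either | success, PA irrelevant |
| any | yes | success, PA irrelevant |
| under 4% | no, or not eligible | failure, PA irrelevant |
| 4% to under 5% | no, or not eligible | depends on PA |

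With weight missing, status is known only if A1C success is met. With A1C missing (baseline in range), it is known only if a weight route is met. With both missing, it is unknown.

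**3. How many participants PA decides (assumed distributions).** Take normally distributed weight loss with mean 2% to 5% and SD 4% to 7%. P(4 ≤ loss < 5) = Φ((5 − mean)/SD) − Φ((4 − mean)/SD).
- Largest: mean 4, SD 4 gives Φ(0.25) − Φ(0) = 9.9%.
- Smallest: mean 2, SD 7 gives Φ(0.429) − Φ(0.286) = 5.3%.

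Removing A1C successes at an assumed 20% to 40%, independent of weight, gives 9.9% × 0.8 = 7.9% down to 5.3% × 0.6 = 3.2%. The overall range, with and without that step, is roughly 3% to 10%.

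**4. How many have all 11 periods (assumed validity q per period).** If misses are independent the share is q¹¹. Power in the subset is Φ(0.15/√(0.5/n) − 1.645), with n per arm = 138 × share and 50% success in both arms.

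| q | Share | Of 276 | Power |
|---|---|---|---|
| 98% | 80% | 221 | 72% |
| 95% | 57% | 157 | 59% |
| 90% | 31% | 87 | 40% |
| 85% | 17% | 46 | 27% |

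The planned power at 138 per arm is 80%. If the baseline period also counts (12 periods), q = 95% gives 0.95¹² = 54%, or 149.

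**5. If misses cluster within people.** Let each person's validity follow a beta distribution with mean q and intraclass correlation ρ, so a = q(1/ρ − 1), b = (1 − q)(1/ρ − 1), and the share with all 11 is B(a + 11, b)/B(a, b).
- q = 95%, ρ from 0.1 to 0.7: 68% to 90% remain (189 to 249 of 276), power 66% to 77%.
- q = 90%, same ρ: 46% to 81% remain.

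**The case against.** **The rule may be meant only for PA outcomes.** The Section 9.4.8 text follows a list of continuous activity measures, for which a PA-complete set is natural. But Section 9.4.2 is the general missing-outcomes section and carries the same rule, and Section 9.4.7 gives the primary endpoint no other. If the rule is PA-only, the composite has no missing-data rule at all. The ambiguity stands; the need to fix the text does too.

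**All 11 periods is a reading.** This is correct: neither section defines 100%. The loss of participants in the working depends on that reading.

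**The subset need not be small.** A reader might infer that only a small remnant would be left. The documents do not support that. They give no compliance rate, misses plausibly cluster, and the protocol has real safeguards: weeks under 75% wear are repeated, compliance is tracked remotely, reminders are sent, each period is paid, and a mail-back option exists. The subset becomes small only if compliance is fairly poor and misses are spread across people.

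**It is only a sensitivity analysis.** A reader might infer that it could overturn the primary result. It cannot: it informs interpretation and does not decide non-inferiority. Nor do the documents show the direction or size of any bias.

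**The PA trigger cannot alter known endpoints.** If PA is imputed and the composite is derived afterwards, known statuses stay fixed in every imputed dataset. This stands, although the plan does not state that order. The trigger's real fault is what it omits.

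**Attrition of 25% is not 25% missing status.** Section 9.3 excludes withdrawals from effectiveness analyses, and Section 7.3 counts participants who stay unreachable as withdrawn. Much of the 25% could therefore leave the analysis rather than be missing within it. The gap concerns anyone retained without 12-month weight or A1C, and the documents do not say how many that would be.

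**Conclusion.** The point holds as a definitional fault. It follows from Section 3.2 alone that PA can decide the composite only for 4% to under 5% weight loss without A1C success. Defining the complete-case set and the imputation trigger on PA is therefore the wrong criterion for the primary endpoint. If 100% means all 11 periods, known endpoints are discarded at any compliance below full.

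The size is conditional. At 95% validity per period, about 57% of the 276 remain with independent misses and about 68% to 90% with clustered misses, while PA decides status for roughly 3% to 10%. Validity, clustering, the weight-change distribution and the A1C success rate are all assumptions. The consequence is a poorly targeted sensitivity analysis with some interpretive weight, and no rule for missing weight or A1C; it is not an invalid primary analysis. It should be corrected.

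**What to change.** Change Sections 9.4.2 and 9.4.8 together.

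- For the primary endpoint, define missingness and the complete-case set on composite status. Status is observed when 12-month weight and A1C determine it, whatever the Actigraphy shows. When PA is needed, status is observed if the months 1 to 11 average rests on at least a pre-stated minimum number of valid wear periods. A minimum is essential, since otherwise one valid week could stand for 11 months.
- In all other cases, multiply impute the missing components (PA, weight or A1C) and derive the composite from the imputed values, so that known statuses stay fixed.
- Keep the PA-complete set only for the PA secondary outcomes, and say there what 100% means.

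The cost is plan wording and modest programming. No new data are needed.
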